7. IP MATERIALS AND MANAGEMENT

7.1. Investigational Product

IP	STI-5656 (Abivertinib maleate)	Placebo
Dose Formulation	Capsule for oral administration	Capsule for oral administration
Unit Dose Strength(s)	50 mg	n/a
Dose to be administered to subjects	200 mg QD (4 capsules once daily)	4 capsules once daily
Route of Administration	p.o. (by mouth)	p.o. (by mouth)
Use	Experimental	
Manufacturer	Shanghai Syn-The-All Pharmaceutical Co. Ltd. (“STA”), a wholly owned subsidiary of WuXi AppTec Co.	Shanghai Syn-The-All Pharmaceutical Co. Ltd. (“STA”), a wholly owned subsidiary of WuXi AppTec Co.
Sourcing	Provided centrally by Sorrento Therapeutics, Inc. or a Sorrento representative	Provided centrally by Sorrento Therapeutics, Inc. or a Sorrento representative
Packaging and Labeling	40 Capsules packaged inside an HDPE bottle and closed with a polypropylene cap.	40 Capsules packaged inside an HDPE bottle and closed with a polypropylene cap.

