- Number of days alive and free of respiratory failure at Day 28
- Number of days with respiratory failure up to Day 28
- Number of days hospitalized up to Day 28
- Number of days in ICU (length of stay) up to Day 90
- Number of days alive outside of hospital up to Day 28
- Number of days alive outside of hospital up to Day 90
- Pharmacokinetics in the study population at 100 mg QD

Exploratory Endpoints:

- See [Section 3.2.3](#)

Subject Population

- ≥18 years with reverse transcriptase polymerase chain reaction (RT-PCR) confirmed infection with severe acute respiratory syndrome coronavirus 2 (SARS-CoV-2)
- COVID-19 pneumonia (documented radiographically) requiring hospitalization; oxygen saturation level <94% on room air or subject requires supplemental oxygen.

Refer to [Section 5](#) for complete eligibility details.

Investigational Product (IP) Description:

Investigational Product (IP) is STI-5656 (Abivertinib maleate)

Planned Sample Size

Approximately 80 subjects will be enrolled in this study, 40 will be randomized to each of two treatment arms.

Treatment Arms

All subjects will receive current standard of care (SOC) treatments.

In this setting, subjects will receive one of two treatments up to Day 14 or until hospital discharge (if sooner):

Arm 1: STI-5656 (100 mg QD starting dose)

Arm 2: Placebo QD

Duration of Study

For subjects, the total duration of the study will be up to 94 days (up to 4 days for the screening period plus up to 14 days for treatment and up to 90 days from randomization for follow-up).

The length of the study will be approximately 7 months (4 months for enrollment plus up to 90 days study duration).

Study Design

This is a Phase 2, randomized, double blind, placebo-controlled, 2-arm multicenter study to assess the safety and efficacy of STI-5656 (capsule administered orally) in the setting of current standard of care (SOC) in subjects with RT-PCR confirmed SARS-CoV-2 (COVID-19) infection and pneumonia (documented radiographically) requiring hospitalization. Subjects must have oxygen saturation levels < 94% on room air or subject requires supplemental oxygen.

Eighty (80) subjects meeting eligibility criteria will receive SOC treatment and will be randomized at a 1:1 ratio to one of two treatment arms

- Arm 1: STI-5656
- Arm 2: Placebo

The starting dose of STI-5656 is 100 mg PO QD administered up to 14 days or until hospital discharge whichever is sooner. Placebo follows the same schedule.

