4. INVESTIGATIONAL PLAN

4.1. Overall Study Design

This is a Phase 2, randomized, double-blind, placebo-controlled, 2-arm multicenter study to assess the safety and efficacy of oral STI-5656 (or placebo) in the setting of current SOC in subjects with RT-PCR confirmed SARS-CoV-2 infection and COVID-19 pneumonia (documented radiographically) requiring hospitalization. Subjects must have oxygen saturation levels <94% on room air or subject requires supplemental oxygen.

Eighty (80) subjects meeting eligibility criteria will be randomized at a 1:1 ratio to one of two treatment arms in addition to SOC treatments:

- Arm 1: STI-5656
- Arm 2: Placebo

The STI-5656 dose is 100 mg p.o. QD administered up to 14 days or until hospital discharge if sooner.

SOC treatments will be collected in the electronic case report form (e-CRF).

Subjects who discontinue at any time after randomization will not be replaced. There is no treatment crossover in this study.

Once subjects provide informed consent, they will have screening assessments performed (up to 4-day screening window). Study Day 1 is the day of randomization. Randomized Subjects should receive their first dose of Study Drug on Day 1.

Subjects will be assessed daily while hospitalized. Subjects in both arms are assessed for adverse events (AEs) and toxicities and all AEs should be reported regardless of treatment arm assignment or causality. Subjects will be contacted on Day 28 to collect any additional AEs and follow-up for unresolved AEs,

SOC treatments will be collected in the electronic case report form (e-CRF) until hospital discharge. Continued outpatient treatment (concomitant medications) will be collected until Day 28. Any investigational medication received will be collected until Day 90. Note: Investigational medicines other than STI-5656 are prohibited up to Day 28 or hospital discharge.

Discharged subjects will be contacted at Day 60 and 90 to ensure survival and collect any experimental treatments and additional hospitalization information since the study hospital discharge. Subjects on Treatment Arm 1 (STI-5656) should be encouraged to remain in the study even if Study Drug is discontinued (for any reason).

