6.2. Investigational Product Administration

Two STI-5656 or matching placebo capsules p.o. QD (two 50-mg capsules) administered up to 14 days or until hospital discharge if sooner.

Study drug capsules should be taken orally with 200-250 mL of water following at least 2 hours of fasting.

If vomiting occurs within 30 minutes after a patient takes the dose and the patients can tolerate the medication, the vomited dose should be made up.

If the subject is unable to swallow, the capsule contents may be flushed down a nasogastric or feeding tube with water.

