## **8.6 Study Drug Administration**

Two STI-5656 or matching placebo capsules p.o. QD (two 50-mg capsules) are administered orally up to 14 days or until hospital discharge if sooner. If vomiting occurs within 30 minutes after a patient takes the dose and the patients can tolerate the medication, the vomited dose should be made up.

If the subject is unable to swallow, the capsule contents may be flushed down a nasogastric or feeding tube with water.

For study drug administration, descriptive statistics of the following parameters will be presented.

- Number of days on study treatment
- Total dose planned
- Total dose administered
- Total dose missed
- Compliance rate, defined as the total dose administered/total dose planned, expressed as a percentage.

Subject listing of study drug administration will be presented.

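### Protocol 7.1 sets the daily dose at 200 mg (four capsules); every other dose statement in the protocol and SAP amounts to 100 mg (two capsules)

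*Protocol*

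**What the plan says.** Protocol 7.1 tabulates the investigational product. Its row for the dose to give reads "200 mg QD (4 capsules once daily" in the STI-5656 column and four capsules once daily in the placebo column. The same table gives a unit strength of 50 mg and bottles of 40 capsules.

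The other dose statements are:

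- Synopsis, treatment arms: "Arm 1: STI-5656 (100 mg QD starting dose".
- Synopsis, study design: "The starting dose of STI-5656 is 100 mg PO QD administered up to 14 days or until hospital discharge whichever is sooner".
- Synopsis, PK endpoint: "Pharmacokinetics in the study population at 100 mg QD".
- Protocol 4.1: "The STI-5656 dose is 100 mg p.o. QD administered up to 14 days or until hospital discharge if sooner". SAP 3.0 gives the same dose.
- Protocol 6.2: "Two STI-5656 or matching placebo capsules p.o. QD (two 50-mg capsules) administered up to 14 days or until hospital discharge if sooner".
- SAP 8.6: "Two STI-5656 or matching placebo capsules p.o. QD (two 50-mg capsules) are administered orally up to 14 days or until hospital discharge if sooner".

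Three further provisions depend on the daily dose. Protocol 6.6 treats any STI-5656 dose above the daily dose the protocol specifies as an overdose. Protocol 10.1 requires an overdose to be reported as an adverse event even when nothing else happened. SAP 8.6 defines compliance as follows: "Compliance rate, defined as the total dose administered/total dose planned, expressed as a percentage".

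**The concern.** The 7.1 row conflicts with all the other dose statements, and it does not look like a typing slip that a reader would notice. The milligram figure matches the capsule count, and the active and placebo cells match each other, so it reads as a usable instruction. It is also in the part of the protocol a pharmacist is likely to consult. Section 7.2, which follows directly, has the site pharmacist dispense the drug, and the label contents listed there include capsule strength but no number of capsules per day.

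Three things are at stake:

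- **Safety.** Hospitalized patients could receive double the intended daily dose.
- **Detection.** A site that takes the protocol dose to be 200 mg would not see a four-capsule day as an overdose. The steps in 6.6 (immediate contact with the medical monitor and at least 24 hours of close observation) and the report required by 10.1 would not be triggered.
- **Pharmacokinetics.** The synopsis specifies the PK endpoint at 100 mg daily, with samples from the first 20 subjects. Four-capsule dosing among them would mix two dose levels.

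**Working it through.** **Inputs.** Unit strength 50 mg and bottle size 40 capsules (Protocol 7.1); four capsules per day (Protocol 7.1); two capsules per day (Protocol 6.2, SAP 8.6); at most 14 days of treatment (Protocol 4.1, 6.2). The totals below assume the full 14 days with no missed doses.

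**Step 1: is each figure consistent with itself?** Daily dose = capsules per day × 50 mg.

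- Protocol 7.1: 4 × 50 = 200 mg, which reproduces the table's own figure.
- Protocol 6.2 and SAP 8.6: 2 × 50 = 100 mg, which agrees with the milligram statements in the synopsis, Protocol 4.1 and SAP 3.0.

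The documents therefore contain two coherent doses, in the ratio 200/100 = 2.0.

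**Step 2: does anything reconcile them?** The synopsis twice calls 100 mg a starting dose, which might suggest a later increase. No section gives an escalation rule, a titration schedule or a 200 mg level, and 4.1 and 6.2 state the dose without that qualifier. The two doses are not reconciled.

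**Step 3: size over a full course.**

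| | Two capsules per day | Four capsules per day |
|---|---|---|
| Capsules in 14 days | 2 × 14 = 28 | 4 × 14 = 56 |
| Total dose | 28 × 50 = 1,400 mg | 56 × 50 = 2,800 mg |
| Days covered by one 40-capsule bottle | 40/2 = 20 | 40/4 = 10 |

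One bottle covers a full course at two capsules per day but not at four. This fits 100 mg as the intended dose but does not prove it.

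**Step 4: effect on reported compliance.** SAP 8.6 fixes the plan at two capsules, so the measure remains defined. A subject given four capsules throughout would show 2,800/1,400 = 200%. If four were given on 7 of the 14 days, an illustrative case, the result would be (7 × 100 + 7 × 200)/1,400 = 2,100/1,400 = 150%.

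**Step 5: effect on overdose reporting.** For an active-arm subject given four capsules on all 14 days, every day exceeds a 100 mg threshold and no day exceeds a 200 mg threshold. If each day is reported separately, that is 14 overdose reports against 0. Protocol 10.1 does not say whether a continuing overdose counts once or daily, so 14 is an upper bound.

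**The case against.** The strongest reply is that the protocol already has a clear operative instruction. Section 6.2 is the section on administering the drug; it gives two capsules in both arms, and the SAP follows it. Section 7.1 concerns supply and materials. This makes misdosing less likely but does not remove the risk, because the row itself states the dose subjects are to receive.

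A second reply is that safeguards exist. Protocol 7.5 requires records that subjects were given the protocol's doses and reconciliation of all drug supplied. Protocol 11.1 has monitors confirm accountability checks. SAP 8.6 lists administration by subject, where four-capsule dosing would show. This partly stands: the proposed dispensing check overlaps with these. However, they may find the error only after exposure, and a check against the protocol's dose is of limited use while the protocol gives two.

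Third, once the row is corrected, 6.6 has a single threshold and restating it is optional. That is right as far as the contradiction goes. There is a separate reason to state the threshold in capsules. Protocol 4.1 intends site personnel to stay blinded and SAP 4.0 keeps the investigator blinded, so a limit expressed only for STI-5656 is hard for them to apply. Whether the pharmacist is blinded is less clear, since 7.2 has that person dispense STI-5656 to Arm 1.

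Fourth, the available protocol is Version 4.0 and the SAP cites Version 5.0. The row may already have been corrected. This limits the finding to Version 4.0 but does not remove the question of how subjects treated under that version were dosed.

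Removing the word for a starting dose from the synopsis is a minor tidying point, and the finding does not depend on it.

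**Conclusion.** The concern holds: the dose row in Protocol 7.1, Version 4.0, is wrong as written and must be corrected. It gives exactly twice the dose stated everywhere else, for both milligrams and capsule count, and the placebo cell has the same error. The doubling follows directly from the documents. The 2,800 mg against 1,400 mg comparison assumes a full 14-day course at four capsules per day.

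Taking 100 mg as the intended dose rests on the agreement of all the other dose statements in the two documents and on the absence of any escalation rule. Two things cannot be settled from the documents: whether Version 5.0 already corrects the row, and whether any subject actually received four capsules.

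**What to change.** 1. In Protocol 7.1, change the active cell to 100 mg once daily (two capsules) and the placebo cell to two capsules once daily.
2. In Protocol 6.6, state the overdose threshold as more than 100 mg, meaning more than two study-drug capsules per day in either arm, so that blinded staff can apply it.
3. Remove the starting-dose wording from the two synopsis statements (minor).
4. Before unblinding, review dispensing records by capsules per day for any four-capsule dosing. Capsule counts do not reveal the arm, and the accountability records required by Protocol 7.5 should supply most of what is needed.

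If Version 5.0 already corrects the row, what remains is item 2 (if the threshold is still unstated) and item 4 for subjects enrolled under Version 4.0.

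The cost is low: two table cells, one sentence in 6.6, one word in each of two synopsis statements, and a blinded records check. Sample size, endpoints and analysis methods are unaffected.

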7.2. IP Packaging and Labeling

STI-5656 will be distributed to the investigational site’s pharmacy. The site pharmacist will dispense STI-5656 to subjects in Treatment Arm 1.

The labels on the study drug bottles will include the following information:

- Protocol Number
- Lot Number
- Name of product and strength of each capsule
- Storage conditions
- Sponsor’s name and address
- The statement: “Caution: New drug-limited by Federal Law to Investigational Use. Keep out of reach of children.”

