An independent data monitoring committee (DMC) is established to evaluate the safety data from the study to ensure the ongoing safety of the study subjects and make recommendations to the Sponsor concerning safety and trial conduct (please refer to the DMC charter for details). A blinded independent statistician will be used to facilitate DMC support. This statistician will have no role in the statistical assessments conducted for the study at its conclusion. Discussions with the independent statistician will be conducted during a closed session during the DMC deliberations. Sponsor, CRO and study site personnel will only participate in the open session.

Unblinding of a given subject to assess an AE stopping rule trigger will be handled in a way to keep the Sponsor, CRO (and staff) and study site personnel blinded.

The study visit schedule and assessments are detailed in [Table 1](#) Schedule of Assessment (SOA).

For subjects, the total duration of the study will be up to 94 days (up to 4 days for the screening period plus up to 14 days for treatment and up to 90 days from randomization for follow-up).

The length of the study will be approximately 7 months (4 months for enrollment plus up to 90 days study duration).

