## 4.0 RANDOMIZATION AND BLINDING

This is a randomized and double-blinded study.

Subjects will be randomized using the IRT on Day 1 to either Treatment Arm 1 (STI-5656 plus SOC) or Treatment Arm 2 (placebo plus SOC) (1:1 ratio) using central integrated response technology (IRT). Subject study discontinuation or study completion should also be registered in the IRT. Sponsor, investigator and the CRO will be blinded throughout the study. The independent statistician who supports the DMC is unblinded.

Emergency unblinding may be requested by the Investigator at any time if needed to properly assess the safety of a patient. The request should be submitted to the CRO and Sponsor's medical monitor.

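### Protocol 7.2 labelling and dispensing text could reveal the arm in a double-blind trial, and 4.1 limits retention encouragement to Arm 1

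*Protocol*

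**What the plan says.** Protocol 4.1 sets the design: "This is a Phase 2, randomized, double-blind, placebo-controlled, 2-arm multicenter study". The same section says that unblinding a subject to assess a stopping-rule trigger must "keep the Sponsor, CRO (and staff) and study site personnel blinded". SAP 4.0 is broader: "Sponsor, investigator and the CRO will be blinded throughout the study". The only unblinded person it names is the independent statistician who supports the DMC.

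Protocol 7.2 is written differently. On dispensing: "The site pharmacist will dispense STI-5656 to subjects in Treatment Arm 1". It gives no matching sentence for placebo or Arm 2. On labels: "The labels on the study drug bottles will include the following information", and the list includes "Name of product and strength of each capsule". The product table in 7.1 gives a unit strength of 50 mg for STI-5656 and n/a for placebo.

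On retention, 4.1 says: "Subjects on Treatment Arm 1 (STI-5656) should be encouraged to remain in the study even if Study Drug is discontinued". The synopsis has the same instruction without naming an arm.

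**The concern.** A bottle label that carries the product name and a strength, when only one of the two products has a strength, can tell the arms apart. A rule to dispense the active drug to Arm 1 presupposes a pharmacist who knows the arm, and the plan does not say that this person is unblinded or how the knowledge is contained.

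The blind matters more than usual here. The primary endpoint is being alive and free of respiratory failure at Day 28, and respiratory failure is defined by use of high-flow oxygen, non-invasive ventilation, intubation or ECMO (Protocol 3.2.1, SAP 9.1). Starting these is a decision made at the site, so knowing the arm can influence it.

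Retention also feeds the endpoint directly. Subjects who discontinue before Day 28 are counted as failures (Protocol 9.4.3, SAP 9.1). Keeping a subject in the study replaces an automatic failure with an observed outcome, which may be a success. Effort directed at one arm can therefore only help that arm.

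**Working it through.** The main check is textual.

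**1. Is the masking procedure described elsewhere?**
- Protocol 6.7, headed Randomization and Blinding, covers only registration and 1:1 randomization in the IRT.
- SAP 4.0 says who is blinded but not how.
- Neither document mentions a masked label, a kit number or an unblinded pharmacist.

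**2. Would a literal label differ by arm?** The label list in 7.2 applies to study drug bottles without distinguishing the arms. With 50 mg for one product and n/a for the other in 7.1, a label filled in product by product would differ. A single label worded to cover both products would not. The list fixes the elements, not the text, so both readings are open.

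**3. Who would see the bottle?**
- Study drug is given at the site to inpatients (6.5).
- The Principal Investigator or a designee is accountable for used and unused supplies (7.4).
- The Investigator keeps a count of bottles and capsules of STI-5656 delivered and administered (7.5).
- Monitors confirm that accountability checks are done (11.1).

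So people whom SAP 4.0 blinds may handle the bottles or review the records, not only the pharmacist.

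**4. Does other text conflict with 7.2?** Yes. Section 6.2 refers to matching placebo capsules, 8.2.2 has STI-5656 or placebo dispensed on Day 1, and 8.2.3 says only Study Drug. Section 6.8 routes emergency unblinding requests to the CRO and the sponsor's medical monitor, which presumes that the investigator does not already know the arm.

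**5. Is the Arm 1 wording isolated?** No. Besides 7.2 and the retention sentence in 4.1:
- the Section 8 introduction ties the discussion about continuing or stopping IP to Arm 1;
- SOA footnote 1 refers to the first STI-5656 dose for a subject assigned to that arm;
- SOA footnote 15 ties STI-5656 or placebo administration to Arm 1.

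Both footnotes are repeated in SAP Appendix 1. In 8.1.10, by contrast, the term correctly defines a randomized arm.

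**6. Scale.** The inputs are 40 subjects per arm and assumed success rates of 95.7% and 70% (Protocol 9.2, SAP 5.0).
- Planned difference: 95.7 − 70 = 25.7 points, which the plan rounds to about 26.
- Two outcomes changed in one arm: 2 / 40 = 5 points.
- Share of the planned effect: 5 / 26 = 19%.

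The 2 is an arbitrary unit. The documents offer nothing from which to estimate how many decisions would be swayed.

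**The case against.** The strongest reply is that the instructions sites follow day to day are blinded in style. Sections 6.2, 8.2.2 and 8.2.3 describe matching capsules and arm-neutral dispensing, and 7.1 puts 40 capsules in the same type of HDPE bottle for both arms. Section 7.2 lists label elements only, and a shared label such as 'STI-5656 50 mg or placebo' would satisfy it. A pharmacist who knows the arm does not by that fact unblind the clinicians who choose respiratory support. SAP 4.0 does not mention pharmacists, and the reference to site personnel in Protocol 4.1 concerns stopping-rule unblinding. A blinded site can also meet both retention sentences by encouraging everyone.

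Most of this stands. It rules out two stronger readings that a reader might infer: that following 7.2 would certainly unblind the sites, and that the retention sentence can be followed only by someone who knows the arm. Neither is supported.

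It does not remove the conflict. The blind would depend on a label wording or a pharmacy arrangement that neither document states, while the text that is stated points the other way.

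**Conclusion.** Section 7.2 of Protocol V4.0 conflicts with the double-blind design and with the protocol's own arm-neutral text. Followed literally, it could disclose the arm to site staff who handle or account for bottles. Section 4.1 conflicts with the synopsis on whom to encourage to stay, and if effort were in fact limited to Arm 1, the failure rule for discontinuation would make the bias favour the active arm. This should be corrected.

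The size of any bias cannot be estimated from the documents. The 5-point figure shows how sensitive a 40-subject arm is and does not predict what would happen.

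Two further inferences go too far. The repeated Arm 1 wording suggests text carried over from an open-label design, but no amendment history in the supplied documents confirms that. Nor do the documents show that any arm was actually revealed, since the label text and any pharmacy instructions are not among them.

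The conclusion rests on Protocol V4.0. SAP 1.0 is based on Protocol V5.0, so 7.2 and 4.1 may since have been corrected; that cannot be checked here.

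**What to change.** First confirm whether Protocol V5.0 already corrects these sections. If it does not:

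- **Protocol 7.2:** specify identical masked labels for both arms, for example 'STI-5656 50 mg or placebo' with a kit number, and dispensing to both arms by IRT kit number. Alternatively, name an unblinded pharmacist and state the safeguards that keep the arm from investigators, bedside staff, monitors and accountability records.
- **Protocol 6.7:** state who is blinded and how.
- **Protocol 4.1:** make the retention sentence apply to all subjects, as the synopsis does.
- **Section 8 introduction and SOA footnotes 1 and 15**, with their copies in SAP Appendix 1: make the Arm 1 wording arm-neutral.
- **Protocol 8.1.10:** leave unchanged. A blanket replacement of the term across Section 8 would damage the arm definition there.

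The cost is protocol and SAP wording plus a label text. Central IRT is already used for randomization, although kit-number dispensing would have to be specified in it. No analysis or sample size changes.
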